6.2.1. Inclusion Criteria

A patient must meet the following criteria to be eligible for inclusion in the study:

1. Males and females ≥ 18 to 75 years of age at screening
2. Previous documentation in the patient's medical records of a fasting serum TG measurement ≥ 1000 mg/dL (11.3 mmol/L) on more than 1 occasion, and all fasting TG values ≥ 500 mg/dL (5.6 mmol/L) at screening

NOTE: TGs will be measured at least twice and at least 4 days apart during the screening period.

3. History of a hospitalization and diagnosis of acute pancreatitis in the past 10 years. (Sponsor may elect to drop the time specification if sufficient enrollment does not occur within a reasonable period of time).
4. On a stable lipid-modifying diet with or without medications (eg, statins, niacin, omega-3 fatty acids). Lipid-modifying diet and doses of medications should be stable for at least 4 weeks (6 weeks for fibrates, 8 weeks for PCSK9 inhibitors) prior to screening
5. BMI index of 18-40 kg/m²
6. Willing to consume no more than an average of 2 standard alcoholic drinks per day and a maximum of 15 standard alcoholic drinks per week for the duration of the study. (A standard alcoholic drink is the equivalent of 12 ounces (355 mL) of beer, 5 ounces (148 mL) of wine, or 1.5 ounces (44 mL) of hard liquor)
7. Willing to refrain from consumption of alcohol for 24 hours prior to each study visit
8. Willing to refrain from cigarette smoking for 24 hours prior to each study visit
9. Willing to consistently maintain previously recommended diet and exercise regimen for duration of the study
10. Willing and able to comply with clinic visits and study-related procedures
11. Provide signed informed consent
12. Able to understand and complete study-related questionnaires

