To reduce variability of TG baseline measurements, baseline at week 0 for patients randomized to active treatment is the geometric mean of the last 2 measurements during the placebo run-in (day -28, day -14) and week 0. Baseline at week 12 for patients switching from placebo to active is the geometric mean of the last 2 measurements during the placebo phase (weeks 6, 8) and first measurement prior to active infusion (week 12). Additional exploratory analyses may be carried out using the average of all available TG observations prior to first dose of active treatment, if no trend over time in those measurements is discernable.

Using the estimate of the log TG mean ratio (week 12/baseline at week 0 for patients randomized to evinacumab and week 24/baseline at week 12 for those randomized to placebo) and the log of the standard deviation derived from the MMRM model, the PP will be calculated using the target percent change from baseline of 40% reduction (ie, log 0.6) in patients without LOF mutations in genes in the LPL pathway. For the probability calculation (ie, $\text{Pr} [\log \text{TG mean ratio (post/pre)}] < \log 0.6$ conditional on this study's TG results), a non-informative normal distribution prior and a normal distribution of the data is assumed. The probability calculation will yield the probability that the actual mean percent decrease is at least the target 40% value, based on the OBSERVED results from the patients without LOF mutations in genes in the LPL pathway.

This fixed sequence design assumes no carryover effect from the placebo run-in period into the active treatment period. This assumption will be verified by assessment of the time course of TG observations during the run-in period. A generally flat or non-decreasing trend over time in the placebo run-in period will be evidence of no carryover effect into the active treatment period and of a useful valid baseline benchmark against which to compare treatment effects based on within-patient comparisons (active treatment period to placebo run-in period). As a sensitivity analysis, the TG reduction and posterior probability analyses of the combined sequence groups will be repeated using the same baseline at week 0. Note that the follow-up period is expected to have

carryover effects from the active treatment period and is included to estimate the time course of those effects. Such carryover effects may also be interpreted as evidence of treatment effects.

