5.7.1. Analysis of Primary Efficacy Variable

The primary efficacy analysis will assess within-patient percent change in TG over 12 weeks of evinacumab treatment (double-blind period for patients randomized to evinacumab and single-blind period for patients randomized to placebo).

The point estimates of TG percent changes between the placebo period and each observation week will be calculated using a Mixed-effect Model for Repeated Measures (MMRM) method in the FAS population. A natural log transformation will be applied to the TG levels prior to

analysis, aiming to provide a relatively normal data distribution (residuals will be examined for normality prior to proceeding with the analysis). The MMRM model will assess within-patient treatment comparisons (using an unstructured covariance matrix), while accounting for baseline TG, study visit, and baseline TG by study visit interaction. Note that study visits will be adjusted to start of evinacumab in order to pool data from both randomized groups of patients for this analysis. Since the comparison of study visits yields the within-patient comparisons of study treatments (ie, week 12 [after 12 weeks of treatment with evinacumab] compared to baseline at week 0 [after 4 weeks of treatment with placebo] for patients randomized to evinacumab and week 24 [after 12 weeks of treatment with evinacumab] compared to baseline at week 12 for those randomized to placebo), contrast and estimate statements will be used to assess treatment effects (least squares [LS] means with confidence intervals) and comparisons (LS mean ratio with CI). Within-patient comparisons will include all patients. In the event the MMRM model covariance matrix does not converge or normality is not achieved with the natural log transformation, then other transformations will be explored, including ranks.

To reduce variability of TG baseline measurements, baseline at week 0 for patients randomized to active treatment is the mean of the 3 log-transformed measurements at day -28, day -14, and week 0. Baseline at week 12 for patients switching from placebo to active is the mean of 3 log-transformed measurements at weeks 6, 8, and 12. Additional exploratory analyses may be carried out using the average of all available TG observations prior to first dose of active treatment, if no trend over time in those measurements is discernable.

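### A flat-looking run-in is weak evidence that the uncontrolled TG baseline is valid, and the optional exploratory baseline admits the screening TG values used for selection

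*SAP*

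**What the plan says.** The primary analysis (Protocol 10.4.3.1, SAP 5.7.1) pools both randomised groups, re-aligns visits to the start of evinacumab, and compares week 12 on drug with each patient's own baseline. For patients randomised to evinacumab, SAP 5.7.1 sets that baseline as the mean log TG at day -28, day -14 and week 0. For the others: "Baseline at week 12 for patients switching from placebo to active is the mean of 3 log-transformed measurements at weeks 6, 8, and 12". No screening value enters either definition.

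On whether the baseline can be trusted, Protocol 10.4.3.1 assumes no carryover from the run-in and states: "This assumption will be verified by assessment of the time course of TG observations during the run-in period". It continues: "A generally flat or non-decreasing trend over time in the placebo run-in period will be evidence of no carryover effect", and also evidence "of a useful valid baseline benchmark against which to compare treatment effects". No estimate, interval or test is named.

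SAP 5.7.1, like Protocol 10.4.3.1, then offers an optional exploratory baseline: the "average of all available TG observations prior to first dose of active treatment, if no trend over time in those measurements is discernable". Screening visits are neither named nor excluded. Inclusion criterion 2 (Protocol 6.2.1) requires every screening TG to be at least 500 mg/dL, and its note says "TGs will be measured at least twice and at least 4 days apart during the screening period". The schedule of events places those samples at visits 1 and 1b.

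The Protocol also plans to repeat the TG reduction for both sequences on the week 0 baseline. SAP 5.7.1 does not repeat this, the list of modifications in SAP 1.2.4 does not declare it dropped, and SAP 10.1 lists no supportive analysis for the primary endpoint.

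**The concern.** With no concurrent control in the primary estimate, a downward drift in TG before the first active dose is counted as drug effect. The Protocol looks for drift in the right direction, since a fall is what would mislead. But it lets the absence of a visible fall stand as evidence, and in a small sample with variable TG a real fall can easily go unseen. The result is then read against a 40% reduction, where a few points matter.

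The exploratory average has a separate problem. Values that had to clear a threshold for entry are on average above the patient's usual level. Putting them into the baseline raises it and enlarges the apparent reduction, and the condition attached (no discernible trend) is again an unseen-trend rule.

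**Working it through.** **Inputs.**
- Log-scale SD of 0.5 for TG change: Protocol 10.2 and SAP 2.2, from phase 1 on-treatment data. No run-in SD is given, so 0.5 is an assumption here. The same sections mention 30–40% on the log scale, hence the variants 0.3 and 0.4.
- N: 15–27 in cohort 3 (closest to the primary subset), up to about 50 overall.
- A 15% fall, log(0.85) = −0.1625, and a two-sided 5% test: chosen for illustration, because the plan states neither.

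**The plan's own figure.** The 90% CI around a 40% reduction is 1 − 0.6·exp(± t·0.5/√N).
- N = 10: t = 1.833, half-width 0.290, giving 19.8% to 55.1%.
- N = 12: t = 1.796, half-width 0.259, giving 22.2% to 53.7%.

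These match the stated 20–55% and 22–54%.

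**Step 1: how often a 15% run-in fall would be missed.** With three equally spaced values, the least-squares slope depends only on last minus first. The trend test is therefore a paired t-test on log(week 0/day -28), with noncentrality 0.1625·√N/SD. At SD 0.5 this is 1.26 at N = 15 (critical t 2.145), 1.69 at N = 27 (2.056) and 2.30 at N = 50 (2.010). The miss rate is the noncentral-t probability between the critical values:

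| SD | N = 15 | N = 27 | N = 50 |
|---|---|---|---|
| 0.3 | 50% | 23% | 4% |
| 0.4 | 69% | 47% | 20% |
| 0.5 | 78% | 63% | 38% |

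A one-sided 5% test at SD 0.5 lowers the N = 50 figure to 27%.

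**Step 2: what an unseen fall would do.** Suppose TG falls 15% linearly on the log scale from day -28 to week 0 and then stops. Relative to week 0, the three log values are 0.1625, 0.0813 and 0, with mean 0.0813. The baseline sits exp(0.0813) = 1.085 times above the week 0 level. A reading of 40% then corresponds to 1 − 0.6 × 1.085 = 34.9% from week 0 in patients randomised to evinacumab. Pooled 2:1 with unaffected placebo switchers, the shift is (2/3) × 0.0813 = 0.0542, and 1 − 0.6 × exp(0.0542) = 36.7%.

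**Step 3: screening values in the exploratory baseline.** Model log TG as a patient mean plus visit error with SD 0.5/√2 = 0.354, so that a ratio of two visits has SD 0.5. Assume a geometric mean of 900–1600 mg/dL and a between-patient log SD of 0.6–0.8 before selection, and require both screening values to be at least 500 mg/dL. None of these distributions is in the documents. In simulation, screening TG exceeds run-in TG by about 1.4–4.5%.

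Screening supplies 2 of the 5 scheduled pre-drug values in patients randomised to evinacumab (visits 1, 1b, 3, 4, 5). The inflation is therefore 1.014^0.4 = 1.0056 to 1.045^0.4 = 1.018. A true 38% reads 1 − 0.62/1.0056 = 38.3% to 1 − 0.62/1.018 = 39.1%. In placebo switchers screening supplies 2 of 10 values (visits 1, 1b, 3–10), so the effect there is about half. Modelling the 1000 mg/dL history rule as well, with medians of 800–1500 mg/dL and the same visit error, a true 40% reads 40.2–40.6%.

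**The case against.** Much of the case for the plan stands.

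- **The screening average is not the primary analysis.** The sentence begins "Additional exploratory analyses may be carried out using the average of all available TG observations prior to first dose of active treatment". A reader might infer that selected screening values inflate the primary result. They do not, because both primary baselines are fixed at visits after screening.
- **The trial is exploratory.** No formal testing is planned, the Protocol says evidence rather than proof, and no decision is gated on the trend reading. A reader might infer that a formal equivalence conclusion is being drawn. The text does not go that far.
- **There is a placebo arm.** SAP 5.7.2 summarises TG change by randomised group, overall and within cohort. In the Step 2 illustration the placebo arm would show a fall of about 1 − 1/1.085 = 7.8% from its run-in baseline. So the information will exist, but the plan does not tie it to the judgement that the baseline is valid.
- **The miss rates are conditional.** No test or alpha is planned, and the SD of 0.5 is described as conservative and is not a run-in SD. At SD 0.3 with 50 patients, a 15% fall would rarely be missed.
- **Regression to the mean.** A reader might infer that the trend check misses regression from screening about 90% of the time. That figure depends on TG distributions the documents do not give: across those tried, the miss rate ran from about 2% to 95%. It is near 90% mainly where the regression, and so the bias, is small. Where regression is 12–22%, the miss rate at N = 50 drops to 2–51%.

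What remains is that the Protocol reads stability from an unquantified flat trend, and that the exploratory wording literally admits the selection values.

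**Conclusion.** The concern holds in a limited form. At cohort 3's planned size, a flat-looking run-in says little about a 15% fall: it would be missed in 63–78% of trials at SD 0.5 and 23–50% at SD 0.3, if judged by a two-sided 5% test. Such a fall would be worth about 5 points on a 40% reading in patients randomised to evinacumab, and about 3 points pooled. These figures rest on an assumed run-in SD, test and size of drift; they show what could go unseen, not that drift is expected.

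The admission of visits 1 and 1b is a drafting fault in an optional analysis. It favours the drug by about 0.3–1.1 points on a true 38% at SD 0.5, under assumed distributions. That is small beside the plan's own 22–54% interval at N = 12. It still deserves correction, because this average is the only alternative TG baseline that SAP 5.7.1 names.

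**What to change.** 1. In SAP 5.7.1 (and the matching sentence in Protocol 10.4.3.1), define the exploratory baseline as the log-scale mean of TG values from day -28 up to the first active dose: run-in visits and, for patients randomised to placebo, the double-blind placebo visits. Exclude visits 1 and 1b, and drop the no-trend condition.
2. In Protocol 10.4.3.1 and SAP 5.7.1, replace the flat-trend and no-trend readings with the estimated log TG change from day -28 to week 0 and its 90% CI. Show it beside the placebo arm's change over the double-blind period. Do not call the baseline verified merely because no trend is visible.
3. Carry the Protocol's week 0 baseline sensitivity analysis into SAP 5.7.1. Only the TG reduction part applies, since SAP 1.2.4 drops the posterior probability.

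Set no pass/fail margin. The documents give none, and a 15% rule could not be met at 27 patients or fewer even with zero observed drift. At SD 0.5 the 90% CI would exclude only falls above 1 − exp(−1.714 × 0.5/√24) = 16.0% at N = 24 and 1 − exp(−1.706 × 0.5/√27) = 15.1% at N = 27.

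The cost is wording plus one estimate and one repeated analysis on data already scheduled. The downside is that with few patients the interval will be wide and may not support any statement about stability.

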5.7.1.1. Sub-group Analyses

To assess the homogeneity of the treatment effect across various subgroups, treatment-by-subgroup factor, time point-by-subgroup factor and treatment-by time point-by subgroup factor interaction terms and a subgroup factor term will be added in the primary MMRM model. Within-patient contrast and estimate statements will be used to assess treatment effects (least squares [LS means with confidence intervals) and comparisons (LS mean ratio with CI). In order to handle imbalances between subgroup factors levels, population weights will be used in the analysis model.

The following subgroups of interest will be evaluated, assuming there are enough patients in each subgroup level to perform the evaluation.

- Cohort assignment (1,2 and 3) as defined at the time of the analysis

A graph will depict the mean (+/- SE) TG concentrations over time for each genotype subgroup.

Nominal p-values for testing mean change from baseline >0 and $>40\%$ at each time point in each cohort may be computed for information purposes. Since this is an exploratory study, control of the overall type-I error is not applicable for statistical testing. Any p-values provided for outcome measures are for descriptive purposes only.

5.7.2. Analyses of Lipids Variables

Descriptive statistical analyses for the lipids defined in Section 4.7.2 will be summarized by treatment group and overall for the study, as well as by treatment group and overall within each cohort in the FAS population.

For descriptive summaries, percent change, and/or when appropriate, absolute change from baseline in conventional (US) and international units will be provided for lipids (LDL-C, Apo B, total-C, TG, non-HDL-C, Lp(a), Apo CIII, Apo A-1, and ratio Apo B/Apo A-1) at each protocol scheduled time point (as defined by e-CRF visit label) for each treatment group. For TGs, measurements on not-fasting patients will be excluded. Observed lipid values will be used, ie, imputation of missing values is not planned. For the evinacumab treated group, within-patient testing of endpoints with a non-normal distribution will use the Wilcoxon signed-rank test and endpoints with a normal distribution will use the paired t-test to evaluate the mean differences between baseline and each protocol visit. The p-value will be provided for descriptive purposes only.

Figures will be produced to support the summary tables for percent change and/or when appropriate absolute change from baseline. The plot will contain mean percent change +/- standard error (SE) through the study visits for each lipid variable (except TG and Lp(a)) by treatment group. For TG and Lp(a), plots will contain the median percent and /or absolute change from baseline along with quartiles (Q1 and Q3) over time by treatment group.

In addition, all lipids measurements (scheduled and unscheduled) will be included in patient listing.

During the SBTP, efficacy variables will be explored through descriptive statistics at each protocol scheduled visit for the total patients administered single-blind study treatment (total), as well as by the patient subgroups of study treatment received in the double-blind treatment period (i.e., evinacumab, placebo). Descriptive statistics will include the observed values of the same parameters as described for each variable in the DBTP, for patients in the single-blind safety analysis set.

For patients receiving evinacumab in the DBTP, a combined summary including both the DBTP and SBTP assessments may be considered, referencing the double-blind baseline for variable calculations. Prolonged time between last dose of double-blind treatment and first dose of single-blind treatment will need to be taken into consideration when combining longitudinal efficacy data. Descriptive statistics will include the observed values of the same parameters as described for each variable in the DBTP, for patients in the double-blind safety analysis set.

5.7.3. Analysis of Other Variables

Descriptive statistical analyses for other endpoints (described in Section 4.7.3) will be summarized by treatment group and overall for the study, as well as by treatment group and overall in the FAS population. For summary tables, only protocol scheduled measurements (as defined by e-CRF visit label) will be included. Patient listings will include all measurements, scheduled and unscheduled.

The summary of results for other variables will be presented separately for the DBTP and SBTP, unless otherwise noted. Summaries for the DBTP will be presented by treatment groups

(evinacumab, placebo) containing patients from the double-blind safety analysis set. Summaries for the SBTP will be presented by all patients and by treatment group in DBTP (i.e., evinacumab, placebo), for patients in the single-blind safety analysis set. No formal inferential testing will be performed for either period. Summaries will be descriptive in nature.

Hs-CRP and HbA1c parameters will be summarized at each protocol-scheduled visit. The medians (with Q1-Q3) will be plotted for hs-CRP and HbA1c. Applying the PCSV criteria at any time during the TEAE period, the number of patients (and percentages) meeting the criteria will be summarized.

Similar tables, except PCSV criteria, will be provided for post heparin LPL activity, APOC2, APOA5, and metabolic parameters.

5.7.4. Analysis of PET Variables

Descriptive statistical analyses for the PET variables defined in Section [4.7.4](#) will be summarized by treatment group and overall for the study, as well as by treatment group and overall within each cohort in the PET population.

For descriptive summaries, raw values, percent change, and/or when appropriate, absolute change from baseline will be provided for PET variables at each protocol scheduled time point (as defined by e-CRF visit label) for each treatment group. Missing values will not be imputed. For the evinacumab treated group, within-patient testing of endpoints with a non-normal distribution will use the Wilcoxon signed-rank test and endpoints with a normal distribution will use the paired t-test to evaluate the mean differences between baseline and each protocol visit. The p-value will be provided for descriptive purposes only

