10.4.3.2. Secondary and Exploratory Efficacy Analysis

Continuous secondary and exploratory endpoints will be analyzed similarly to the primary endpoint, except PP will not be computed. Binary endpoints will be summarized by counts and percents. Triglyceride mean percent change from baseline at each observation week will be summarized. Triglyceride mean percent change from baseline at each observation week will be analyzed and estimated for genetic mutations affecting LPL function (eg, homozygous LPL null [total LOF], heterozygous LPL null, with no LPL null gene mutations subgroups).

For the FDG-PET endpoint, comparisons will be within the evinacumab-treated patients in the double-blind period (week 12 vs week -2 for post/pre) and between the treatment groups in the double-blind period (week 12 vs week -2 for evinacumab in comparison to week 12 vs week -2 for placebo). In order to yield corresponding results, the MRI readout will be analyzed similarly as the FDG-PET endpoint. In addition, combining all evinacumab post/pre observations from the double-blind period (week 12 vs week -2) and the single-blind post/pre (week 24 vs week 12) for the patients who received placebo in the double-blind period, and post/pre (week 24 vs week -2 and week 24 vs week 12) for patients randomized to evinacumab during the double-blind period.

Summary statistics may be computed for time points beyond week 12 for the TG and continuous and exploratory endpoints in the patients randomized to evinacumab.

Summary statistics will be computed for the End of Day symptom diary and the symptom and dietary impact measure. These measures will also be psychometrically analyzed; this will be outlined in a separate psychometric analysis plan.

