	
analysis.”
 
“To reduce variability of TG baseline measurements, baseline at week 0 for patients randomized to active treatment is the geometric mean of the last 2 measurements during the placebo run-in (day -28, day -14) and week 0.”
	mean (arithmetic), since the log-transformed geometric mean of measurements is equivalent to the arithmetic mean of log-transformed measurements.
5	10.4.3.2 Secondary and Exploratory Efficacy Analysis	
SAP Section 5.7.2, 5.9 to 5.12:
 
Analyses for each secondary and exploratory endpoint are specified in the corresponding sections for each endpoint.The statement that “Continuous secondary and exploratory endpoints will be analyzed similarly to the primary endpoint” was deleted since for some continuous variables MMRM model may not converge due to the small number of visits/observations
6	10.4.5.3 Treatment Exposure The duration of exposure during the study will be presented and calculated as: (Date of last evinacumab injection - date of first evinacumab injection) + 24 weeks (length of follow-up period)	
SAP Section 4.6:
 
Duration of exposure was divided to double-blind and single-blind period and the duration definition was changed to “...+28 days/7” to be consistent with other evinacumab studies.

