2.2. Sample Size and Power Considerations

Percent change in TG is analyzed based on log (post/pre) transformation, allowing for a normal distribution of the data. Standard deviations (SD) of raw percent changes up to 13% are akin to moderate SD on the log scale (30-40%). For the statistical precision calculations, a log-scale SD of 0.5 was used based on available evinacumab phase 1 data and is assumed to be conservative. With N=10 patients, the 90% confidence interval (CI) for an estimated mean reduction in triglycerides of 40% is approximately 20% to 55%. With N=12, the CI is 22% to 54%. A sample size of 24 is considered adequate to analyze the percent change in TG in the 3 genetic cohorts. Assuming a 20% drop out rate, approximately 30 patients will be needed to assess TG. Additional patients (up to a maximum of approximately 50 patients) will be enrolled with the intent to explore the effect of evinacumab on development of pancreatitis.

For the FDG-PET uptake signal SUVmax, prior data on steroid-treated patients yielded a natural log-scale SD of change of 0.66 ([Shigekawa 2010](#)). This yields 80% power to yield a statistically significant ($\alpha=0.05$, 1-sided) change from baseline within the N=16 evinacumab-treated patients if the TRUE underlying geometric mean ratio (post/pre) is 0.65 (back-transformed from the log-scale; ~35% reduction). For comparison to the N=8 placebo-treated patients, assuming log-scale SD=0.15 for placebo based on reproducibility data, and 0.66 for evinacumab, there is 80% power if the TRUE underlying geometric mean ratio (GMR) of GMR's (evinacumab post/pre divided by placebo post/pre) is 0.64 (~36% reduction).

[figure not shown]
For the key MRI endpoint "mean f", which is the weighting coefficient between contrasting MRI regions (Klauss 2015), reported summary statistics yielded an SD estimate at most 5.96 for change from baseline. With this assumed SD, the N=24 patients with evinacumab post- and pre-values have 80% power to yield a statistically significant (alpha=0.05, 1-sided) change from baseline if the TRUE underlying mean change is 3.12 (~30% from baseline 10.5, which was observed by Klauss [Klauss 2015]). For the between-treatment comparison (N=16 evinacumab vs N=8 placebo), there is 80% power if the TRUE difference is 6.62 (~63% of the 10.5 baseline value observed by Klauss [Klauss 2015]).

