4.7.4. PET Variable(s)

The F-FDG PET endpoints are listed below:

- Percent change in pancreatic 18F-FDG standardized uptake values SUVmax and SUVmean from baseline at week 12
- Percent change in 18F-FDG-PET target to background ratio [TBR] in carotids and/or aorta atherosclerotic plaques at week 12
- The change in pancreatic ¹⁸F-FDG Ki or Kpatlak from baseline at week 12

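### SAP 2.2 states 80% power for the SUVmax change on the log-ratio scale, but SAP 4.7.4 and 5.7.4 use percent or raw change, where power on percent change is about 57% at N=16

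*SAP*

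**What the plan says.** **Sample size (SAP 2.2, the same in Protocol 10.2).** The PET calculation is on the natural-log scale: "prior data on steroid-treated patients yielded a natural log-scale SD of change of 0.66". The text continues: "This yields 80% power to yield a statistically significant" (one-sided alpha 0.05) "change from baseline within the N=16 evinacumab-treated patients if the TRUE underlying geometric mean ratio (post/pre) is 0.65", which it glosses as "back-transformed from the log-scale; ~35% reduction".

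**Endpoint (SAP 4.7.4).** "Percent change in pancreatic 18F-FDG standardized uptake values SUVmax and SUVmean from baseline at week 12".

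**Analysis (SAP 5.7.4).** The summaries are "raw values, percent change, and/or when appropriate, absolute change from baseline will be provided for PET variables at each protocol scheduled time point". A later sentence in the section tests the evinacumab group within patients, by Wilcoxon signed-rank if the endpoint is non-normal and by paired t-test if it is normal. The stated target is the mean difference between baseline and visit. No log transformation is named, sidedness is not given, and the p-value is declared descriptive.

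**Where the log scale stood before.** Protocol 10.4.3.2 says: "Continuous secondary and exploratory endpoints will be analyzed similarly to the primary endpoint, except PP will not be computed". The primary endpoint is log-transformed (Protocol 10.4.3.1). SAP 1.2.4, item 5, deletes that sentence "since for some continuous variables MMRM model may not converge due to the small number of visits/observations". The item does not mention scale.

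**The concern.** The 80% belongs to a one-sample test on log(post/pre), and the SAP no longer contains that test for PET. A post/pre ratio with a log SD of 0.66 is strongly right-skewed. On the percent-change scale a few patients with large rises pull the mean up and inflate its standard error, and they also take the highest ranks in a signed-rank test. Power is therefore lost on either branch of the SAP's rule.

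The reported effect is affected as well. Protocol 8.2.4.1 treats a 30% reduction in pancreatic uptake as clinically significant. If the mean percent change is what gets read against that benchmark, an effect of the size used to plan the trial would usually appear to miss it.

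The reason given for deleting the protocol's sentence does not bear on PET. The schedule of events has one baseline and one post-baseline PET scan, so no MMRM is needed and convergence is no ground for leaving the log scale.

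**Working it through.** **Inputs (SAP 2.2).** N = 16; GMR = 0.65; log SD = 0.66; alpha = 0.05, one-sided.

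**1. The plan's figure.** One-sample t-test on log(post/pre), df = 15:

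- effect = ln 0.65 = -0.431
- standard error = 0.66/√16 = 0.165
- noncentrality = 0.431/0.165 = 2.61
- power from the noncentral t = **80.1%** (stated: 80%)

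As a cross-check, the between-arm figure (16 v 8, SD 0.66 and 0.15, ratio of GMRs 0.64) gives 79.7% by a Welch t-test. Both PET power statements are therefore log-scale calculations.

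**2. The SAP's tests on percent change.** Simulate L ~ Normal(ln 0.65, 0.66) and analyse exp(L) - 1:

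| Analysis, N=16 | One-sided 0.05 | Two-sided 0.05 |
|---|---|---|
| t-test on log ratio | 80% | 68% |
| t-test on percent change | 46% | 37% |
| Wilcoxon on percent change | 57% | 43% |
| Test chosen by a Shapiro-Wilk check | 57.5% | 44% |

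The SAP does not say how normality is judged; Shapiro-Wilk at 0.05 is an assumption. About 60% of simulated samples fail it, so the rule mostly leads to Wilcoxon, and about 57% is the relevant figure. The two-sided column is there because SAP 5.7.4 does not state sidedness.

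**3. Sensitivity to N and SD (percent change, one-sided).** N=16 is two thirds of the 24 evaluable patients. If about 50 are enrolled, two thirds is about 33; after the plan's 20% dropout, 33.3 × 0.8 = 26.7, or about 27.

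| | Wilcoxon, percent change | t, percent change | t, log ratio |
|---|---|---|---|
| SD 0.66, N=16 | 57% | 46% | 80% |
| SD 0.66, N=27 | 77% | 56% | 95% |
| SD 0.66, N=33 | 84% | 60% | 98% |
| SD 0.50, N=16 | 84% | 78% | 95% |

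At a log SD of 0.3 the loss is negligible.

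**4. Raw differences.** These need the joint distribution of baseline and ratio, which the documents do not give. The assumed baseline is lognormal around an SUV of 4.

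- Ratio independent of baseline, baseline CV 0 to 0.5: t 45-47%, Wilcoxon 57%.
- Log ratio correlated -0.3 to -0.7 with log baseline, CV 0.3 to 0.5: t 54-77%, Wilcoxon 62-76%.
- Correlation +0.3: t 34-38%, Wilcoxon 50-53%.

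The overall range is about 34-77%, so no single figure is defensible on this scale.

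**5. The effect estimate.** For a lognormal ratio the arithmetic mean is GMR × exp(SD²/2):

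- 0.65 × exp(0.66²/2) = 0.65 × 1.243 = 0.808, a mean percent change of **-19%**
- the sample median percent change averages about **-34%**

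The chance that the observed GMR shows at least a 30% fall is Φ[(ln 0.70 - ln 0.65)/0.165] = Φ(0.449) = 67%. In simulation the observed arithmetic mean percent change reaches -30% in only about a quarter of trials.

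**The case against.** **PET is secondary and its p-values are descriptive.** Protocol 10.1 plans no formal testing, and no decision rule depends on PET power. This stands, and it limits the consequence. It does not make the 80% true of the specified test, and it does not bear on the effect estimate.

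**The mean need not be the reported figure.** SAP 5.7.4 does not say which summary statistic is used. Protocol 10.4 allows a geometric mean and a log-scale SD as well as a median, and SAP 1.2.4 does not list that section as changed. A median or geometric mean beside the arithmetic mean would largely show the true picture. This stands, but SAP 5.7.4 commits to neither and names mean differences as the target of the test.

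**A reader might call -19% biased.** It is not. It is a correct arithmetic mean of percent change, which is a different quantity from the geometric change used to plan the study.

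**A reader might infer an apparent rise in inflammation under no drug effect.** Applying SD 0.66 to a null effect gives exp(0.66²/2) - 1 = +24%. The plan's inputs do not support this. The 0.66 comes from steroid-treated patients; for patients without active treatment the plan uses 0.15, and exp(0.15²/2) - 1 = +1%. An inert drug would look like placebo.

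**A reader might take 46% as the SAP's power.** That is the t-test alone, a branch that the SAP's rule leaves in most skewed samples.

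**The link to the deleted protocol sentence is partly inferred.** Item 5 of SAP 1.2.4 points to SAP 5.7.2 and 5.9 to 5.12, not to 5.7.4. The loss of the log scale for PET is therefore an undeclared consequence at most; the SAP does not state it as a decision.

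**Conclusion.** The concern holds in this form. SAP 2.2 powers SUVmax on the log ratio, and SAP 4.7.4 and 5.7.4 define and test PET on other scales. On percent change, with the plan's own inputs and one-sided 0.05, the SAP's rule has about 57% power at N=16 against the stated 80%. That rests on a lognormal ratio and a log SD of 0.66. A larger evinacumab group narrows the gap, as does a smaller SD. No firm figure can be given for raw differences.

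The effect estimate matters as much as the power. At the design effect the mean percent change is expected to fall short of the protocol's 30% benchmark, while the geometric mean ratio and the median are expected to exceed it. The documents do not support more than this: no confirmatory conclusion is at risk, and no false signal of harm is predicted if the drug does nothing.

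**What to change.** In SAP 4.7.4 and 5.7.4, analyse SUVmax and SUVmean as log(week 12/baseline). Report the geometric mean ratio with its confidence interval for each arm, and use a one-sample t-test on the log ratio in the evinacumab arm, stating sidedness. Percent change is still available as 100 × (GMR - 1); give medians alongside and keep raw values as listings. Add a line to SAP 1.2.4 recording the scale used for PET.

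If the sponsor prefers percent or raw change, restate the power in SAP 2.2 for that scale and test, with the assumptions shown.

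The p-values stay descriptive either way. The cost is a few lines of SAP text and one transformation in the program; no data collection changes.
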